Traditional suture-based fixation is known to cause significant patient discomfort, predominantly at the site of skin suture fixation, where any pull on the drain tubing is transmitted to a focal point on the skin. Over time, this can result in significant skin irritation, inflammation and pain, skin erosion, loosening of the drain, suture failure, and possibly even early, unintended loss of the drain. Early loss of a drain, in turn, can lead to complications of seroma and/or infected abscess. In a survey of 40 Wake Forest Plastic Surgery Patients with drains, patients asked were to rate their experience with surgical drains compared to their expectations on a sliding scale. The majority of patients reported experiences that were worse than or as expected (Figure 1). When specifically asked about irritation at the drain site, 33 of 40 patients rated comfort and pain as worse than

or as expected (Figure 2). With the known negative patient experiences associated with suture-based drain securement, there is a need for novel drain securement techniques and devices that can improve patient comfort and drain security.

The K-Lock® Device is a novel sutureless drain securement device that may improve patient experiences with surgical drains. The K-Lock Device is an FDA Class I device exempt from 510k requirements.

OBJECTIVES:

To evaluate the feasibility, safety and efficacy of a novel suture-less drain securement device (K-Lock) via direct comparison to suture-based techniques.

To evaluate patient satisfaction with their surgical drain sites post operatively.

DESIGN:

Randomized controlled trial

SETTING:

Academic Medical Center

SUBJECTS SELECTION CRITERIA:

Inclusion Criteria:

Age 18 or older

Patient of the Department of Plastic and Reconstructive Surgery

Able to sign English language Consent form

Undergoing any of the following procedures requiring placement of 2 or more drains (preferably bilateral) including:

- Breast reconstruction
- Bilateral Breast Reduction
- Abdominoplasty
- Body Contour surgery (e.g. panniculectomy, brachiplasty, thighplasty)

Exclusion Criteria:

Patients with unilateral drain placement Unable to sign English language consent form Allergy to Tegaderm Dressing Allergy to skin adhesives

SAMPLE SIZE:

We plan to enroll 40 patients allowing analysis of 80 (20 paired) drain sites: 40 prototype drain securement sites and 40 suture-based drain securement sites.

INTERVENTIONS AND INTERACTIONS:

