Patients will be randomized to either A) left side K-Lock with right side suture-based technique or B) right side K-Lock with left side suture-based technique. Randomization will occur before study initiation with group A or group B being assigned to a study enrollment number.

Preoperatively:

The novel suture-less prototype device will be described and/or demonstrated to the patients, and the rationale for its development will be explained. They will have opportunity to ask questions and then they will be invited to participate in the study.

Written informed consent will be obtained.

Intraoperatively:

Surgical drains will be placed per the usual routine of the surgeon. However, prior to definitive fixation, the drains will be temporarily secured to the skin with a towel clamp and covered and/or positioned out of the way to allow for closure of surgical incisions. Definitive drain fixation will occur when all of the pertinent incisions are closed and dressed. At that time, each drain will be secured according to the randomization scheme.

The amount of **time it takes to secure and dress each drain will be recorded** using a time-stamped video (e.g. iphone). No identifying data/information will be recorded, only the zoomed field pertinent to drain securement. For the prototype drain securement device, the 'video clock' will be started when the device is passed to the surgeon and stopped when the device/dressing is attached in place. For the standard suture-based technique, the 'video clock' will be started when the suture is passed to the surgeon and will be stopped when the dressing has been placed and secured. Use of a Biopatch with the drain will be up to the surgeon's preference. The standard dressing for the suture-based techniques will include a split 4 x 4 dressing covered with a tegaderm. All dressing materials must be ready and available prior to handing the surgeon the suture/device.

Postoperatively:

The time until drain removal will be recorded for both groups.

On postoperative visit(s) on which a drain is removed, patients will complete a **survey** about their experience with the pertinent securement method/drain site.

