Feasibility and **ease of use** of the novel drain device will be evaluated by evaluation of video recordings, qualitative feedback obtained from surgeons and/or O.R staff and nurses that handle and observe use of the device. Any failed application of the device will specifically be noted. In the event that a test device will need to be replaced for continued drain securement because the device has become loose or otherwise fouled, the replacement process will be performed by clinic staff using the IFU for such, and will be video recorded

Safety of the novel drain device will be evaluated by inspecting device sites for instances of skin irritation at each office visit and at the time of drain removal, including photographs of drain sites immediately before and after removal. It will also be assessed by feedback obtained in the patient surveys.

Postoperative review of patient charts will collect the following information up to 1 month from the removal of a subject's final drain:

- Date of drain removal (i.e. duration of drain)
- Accidental vs Planned drain removal
- Loosening of the drain
- Any need for new device/new suture material to secure drain
- Reinsertion of drain
- Patient calls to triage regarding drain issues/concerns and the estimated or actual time/effort devoted to each issue/concern by clinic staff
- Photos of the drain site at time of removal

As a follow-up to previous study activities, subjects will be contacted either by phone or at future clinic visits to gauge their interest in further participation. Subjects will be asked to have pictures taken of their drain sites and to fill out a survey to measure their satisfaction with their surgical drain sites further out from their procedures. Pictures will be attained at a scheduled research visit or a regular clinic visit if possible. A blinded evaluator will view the photos to assess in addition to the subject's self-reported outcomes. The tool the subjects will complete is the Patient and Observer Scar Assessment Scale (POSAS).

OUTCOME MEASURES:

Primary:

Feasibility

Secondary:

Safety

Satisfaction

ANALYTICAL PLAN:

Results will be analyzed initially using descriptive statistics. Comparison between groups will be done using chi square tests for proportions, and t-tests or ANOVA procedures for continuous variables. Regression analysis will be performed to identify independent outcome predictors. Other inferential statistical analysis will be conducted as appropriate.

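### Each patient receives both securement methods, but the plan names chi-square tests for proportions and does not say whether t-tests, ANOVA or regression will respect the pairing

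*Combined protocol and SAP*

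**What the plan says.** **Design.** Under Interventions and Interactions: "Patients will be randomized to either A) left side K-Lock with right side suture-based technique or B) right side K-Lock", with suture on the left in arm B. During surgery, "At that time, each drain will be secured according to the randomization scheme". Eligible procedures are those "requiring placement of 2 or more drains (preferably bilateral"), and unilateral drain placement is an exclusion.

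**Outcomes by drain or site.** Time to secure and dress is recorded for each drain. "The time until drain removal will be recorded for both groups". At drain removal, patients complete a survey "about their experience with the pertinent securement method/drain site". Chart review collects accidental versus planned removal, loosening, need for new securing material, and reinsertion. On skin irritation the text is narrower: "Safety of the novel drain device will be evaluated by inspecting device sites for instances of skin irritation at each office visit".

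**Sample size.** "We plan to enroll 40 patients allowing analysis of 80 (20 paired) drain sites", split as 40 sites per method.

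**Analysis.** After descriptive statistics, the Analytical Plan says: "Comparison between groups will be done using chi square tests for proportions, and t-tests or ANOVA procedures for continuous variables". It adds regression for outcome predictors and other inferential analysis as appropriate. It names no matched or paired test, repeated-measures form, mixed model, GEE or patient-level term.

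**The concern.** Two sites on the same patient share that patient's skin, surgeon, operation, activity and handling of drains, so their outcomes are likely to be correlated. The within-patient design exists to remove that shared variation. A Pearson chi-square test on 40 v 40 sites uses only the two totals. It ignores which patients had the event on both sides, on one side or on neither, so its standard error is wrong for the design.

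At stake are the secondary comparisons of safety and satisfaction, within an objective framed as a direct comparison of K-Lock with suture. A real difference, whether a benefit or a harm of the device, could be missed. And because the plan does not settle the choice between paired and unpaired tests, that choice could be made after the data are seen.

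**Working it through.** **1. Count of pairs.** 40 patients × 2 methods = 80 sites, which agrees with the plan. 80 / 2 = 40 pairs, which does not agree with the 20 in the same sentence. The plan gives no alpha, power, effect size, SD or event rate, so the sample size itself cannot be reproduced.

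**2. Inputs for the illustration.** From the plan: 40 patients, one site per method. Assumed, because the documents are silent: two-sided 5%; event rates as shown; within-patient correlation of the binary outcome (phi) 0, 0.3 or 0.5.

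**3. Why pairing matters.** With rates p₁ and p₂ and n pairs, the variance of the difference in proportions is

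[p₁(1−p₁) + p₂(1−p₂) − 2·phi·√(p₁(1−p₁)p₂(1−p₂))] / n.

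The unpaired test omits the last term. At equal rates the true variance is (1−phi) times the one it uses, so its large-sample size is 2[1 − Φ(1.96/√(1−phi))]: 5.0% at phi 0, 1.9% at 0.3 and 0.6% at 0.5.

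**4. Exact enumeration, 40 pairs.** All matched 2×2 tables were enumerated, with P(both) = p₁p₂ + phi·√(p₁(1−p₁)p₂(1−p₂)). Chi-square is the uncorrected Pearson test on 40 v 40 sites. McNemar is (b−c)²/(b+c) against 3.84, where b and c are the discordant counts, without continuity correction.

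| Rates | Quantity | Test | phi 0 | phi 0.3 | phi 0.5 |
|---|---|---|---|---|---|
| 30% v 30% | size | chi-square | 4.8% | 1.9% | 0.6% |
| 30% v 30% | size | McNemar | 5.0% | 4.3% | 4.4% |
| 30% v 10% | power | chi-square | 0.63 | 0.65 | 0.68 |
| 30% v 10% | power | McNemar | 0.60 | 0.76 | 0.96 |
| 20% v 5% | power | chi-square | 0.57 | 0.58 | not possible |
| 20% v 5% | power | McNemar | 0.51 | 0.69 | not possible |

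The phi 0.5 entry for 30% v 10% is close to the largest phi those rates allow: (0.10 − 0.03)/√(0.21 × 0.09) = 0.51. It should be read as an extreme. If only 20 pairs were analysed, power for 30% v 10% at phi 0.3 would be 0.33 (chi-square) and 0.45 (McNemar).

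**5. One data set, two answers.** Suppose 14/40 v 7/40. Pooled rate 21/80 = 0.2625; chi-square = 0.175² / (0.2625 × 0.7375 × 2/40) = 3.16, p = 0.075, whatever the overlap. If 5 patients are positive on both sides, b = 9 and c = 2, so McNemar = 49/11 = 4.45, p = 0.035. If 3 are, b = 11 and c = 4, so 49/15 = 3.27, p = 0.071.

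**6. Continuous outcomes, only if the t-test is run unpaired.** By simulation of 40 pairs with a 0.5 SD difference, unpaired v paired power is 0.60 v 0.59, 0.61 v 0.74 and 0.64 v 0.87 at correlation 0, 0.3 and 0.5.

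**7. Which paired binary test.** For uncommon events the choice matters. At 15% v 3% and phi 0.3, power is 0.52 for chi-square, 0.63 for McNemar without correction and 0.50 for mid-p McNemar. At 5% on both sides and phi 0 / 0.3 / 0.5, size is 4.3 / 1.6 / 0.5% for chi-square and 1.5 / 0.6 / 0.2% for mid-p.

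**The case against.** *The plan never says unpaired.* True. McNemar's statistic is also referred to a chi-square distribution, the Sample Size section uses the word paired, and the closing clause leaves room for other methods. For t-tests and ANOVA this stands: both can be run paired, and groups can mean the two methods, so the gap there is specification and not error. For proportions it stands only in part. A chi-square test of proportions between groups ordinarily means the independent-samples test, and a clause permitting other analyses prespecifies none.

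*The error is conservative, and the primary outcome is feasibility.* Both stand, and they limit the point. A reader might infer that the chosen test risks a false claim for the device. With one drain per side and positive correlation it does not; its size falls below 5%. Inflation would need several drains per side, or stacked sites in a regression on patient-level predictors, to be treated as independent. The plan allows more than two drains and has no rule for them, but it does not say they will be treated that way.

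*Other inferences that go too far.* One might add that confidence intervals will be too wide, but the plan states no intervals. One might also conclude that skin irritation is never recorded at suture sites. The inspection sentence names device sites, but it goes on to photographs of drain sites, and the survey covers each method, so this is an open question.

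*The harm depends on assumed correlations and rates.* It does. At phi 0 nothing is gained by pairing, and the largest gains need high correlation.

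**Conclusion.** The concern holds as follows. The design is within patient; the test named for proportions, on its ordinary reading, does not fit matched outcomes; and pairing is unstated for t-tests, ANOVA and regression. The consequence is lost power in the secondary comparisons, in either direction, with little effect on the primary outcome. At an assumed phi of 0.3 and 30% v 10%, the loss is about 0.11 (0.76 − 0.65); at phi 0 there is none. These figures rest on 40 pairs, one drain per side, two-sided 5%, and correlations and rates that the documents do not supply. It should be fixed, but it does not threaten the trial's validity.

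**What to change.** Replace the comparison sentence in the Analytical Plan with:

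> K-Lock and suture will be compared within patient. Binary outcomes recorded at both sites: McNemar test without continuity correction, with a paired risk difference and 95% CI. Continuous outcomes: paired t-test or Wilcoxon signed-rank test. Regression, and any analysis with more than one drain per side, will use a mixed model or GEE clustered on patient.

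If a mid-p or exact McNemar test is preferred, state that either can have less power than chi-square for uncommon events.

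Two related corrections:
- In the Sample Size section, change the 20 to 40 pairs, or explain what 20 means.
- State whether skin irritation is recorded at suture sites too, and compare it between methods only if it is.

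**Cost.** Wording only; no added patients. The small downside is that at low correlation with uncommon events the paired test has slightly less power (20% v 5%, phi 0: 0.51 v 0.57).

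### The analysis plan does not specify pairing or a side (A/B) term although side is what is randomised, so a consistent left-right difference would widen the K-Lock comparison and, at an unequal realised split, shift it

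*Combined protocol and SAP*

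**What the plan says.** - **Randomised factor.** The section Interventions and Interactions defines the two allocations as follows: "Patients will be randomized to either A) left side K-Lock with right side suture-based technique or B) right side K-Lock with left side suture-based technique". Each patient therefore contributes both methods, and chance decides only the side.
- **Allocation list.** On how the list is made, the same section says only this: "Randomization will occur before study initiation with group A or group B being assigned to a study enrollment number". No ratio, blocking, stratification or other balance rule is stated.
- **Sample Size.** The planned count reads "We plan to enroll 40 patients allowing analysis of 80 (20 paired) drain sites". The section then splits these sites equally by method, 40 for K-Lock and 40 for suture.
- **Analytical Plan.** The sentence that governs the comparison is "Comparison between groups will be done using chi square tests for proportions, and t-tests or ANOVA procedures for continuous variables". After it come two open clauses. The first concerns regression: "Regression analysis will be performed to identify independent outcome predictors". The second is a general allowance for further tests: "Other inferential statistical analysis will be conducted as appropriate". Neither names a variable.
- **Inclusion Criteria.** Eligible operations are described as "requiring placement of 2 or more drains (preferably bilateral) including" four types of operation, so a patient may have more than two drains.

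The documents give no alpha, power, effect size, SD or expected left-right difference.

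**The concern.** The K-Lock effect is estimated inside each patient, and the tests named are those for independent groups. Adding pairing is the first repair, but it does not finish the job. Pairing removes what a patient's two sides share. It does not remove a systematic difference between left and right, for example one that comes from operator handedness. That difference enters the K-Lock-minus-suture contrast with a plus sign in group A and a minus sign in group B.

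Two consequences follow if the analysis ignores A/B. The alternating sign adds spread to the paired differences, so intervals widen. If A and B end up unequal in number, the plus and minus signs do not cancel and the estimate moves. The protocol's objective includes a direct comparison with suture-based techniques, and with 40 patients there is little precision to spare.

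**Working it through.** **Inputs from the documents.** 40 patients; one K-Lock and one suture side each; A = K-Lock left, B = K-Lock right.

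**Assumptions, because the documents give none.** Two-sided alpha 0.05; residual SD of the within-patient difference set to 1; effect tau = 0.455 SD; left-minus-right difference L = 0.25, 0.5 or 1 SD; simple 1:1 allocation where the split is treated as random.

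**1. The plan's own count.** 40 × 2 = 80 sites, which reproduces. The same count gives 40 within-patient pairs, not the 20 in brackets; that figure needs reconciling. The work below uses 40 pairs.

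**2. Model.** Let D be the K-Lock-minus-suture difference in a patient. Its mean is tau + L in A and tau − L in B.

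**3. Shift of the plain paired mean.** Given the split, it is L × (nA − nB)/40. At 20:20 it is 0. At 24:16 it is 8/40 = 0.2 × L. At 26:14 it is 12/40 = 0.3 × L. For Binomial(40, 0.5), the probability of exactly 20:20 is 12.5%, of 24:16 or worse 26.8%, and of 26:14 or worse 8.1%. Averaged over that distribution, the shift is zero.

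**4. Standard error of the plain paired mean.** Near balance the SD of D is √(1 + L²): √1.0625 = 1.031, √1.25 = 1.118 and √2 = 1.414. The standard error is thus about 3%, 12% and 41% wider.

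**5. Error rate and power.** With L = 0 the paired t-test has noncentrality 0.455 × √40 = 2.88 on 39 df, which gives 80% power. Simulation with 60,000 trials per scenario gives the following for the paired t-test without side:

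| L | Power, 20:20 | Type I, 20:20 | Power, simple allocation | Type I, simple allocation | Type I given 24:16 | Type I given 26:14 |
|---|---|---|---|---|---|---|
| 0.25 | 78.4% | 4.4% | 77.7% | 4.9% | 5.3% | 6.7% |
| 0.5 | 72.5% | 2.9% | 70.8% | 5.0% | 6.0% | 10.8% |
| 1 | 50.3% | 0.5% | 50.7% | 4.9% | 6.5% | 19.3% |

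**6. With side in the model.** The estimate is (mean of D in A + mean of D in B)/2, on 38 df. L cancels at any split. In the simulation its type I error is about 5% for each L in the table. Power is about 80% at 20:20, 78 to 79% at 24:16 and 76% at 26:14.

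**7. Cost of adjusting.** The variance is (1/4)(1/nA + 1/nB). At 24:16 this is 0.25 × (0.04167 + 0.06250) = 0.02604, against 1/40 = 0.025, a ratio of 1.04. If L = 0, that 4% and one degree of freedom are the net loss.

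**The case against.** - **The estimate is protected by randomisation.** A reader might infer that omitting side biases the K-Lock effect. The design does not support that: side is randomised, so over simple allocation the paired estimate is unbiased and its test keeps about 5% error. The shift exists only given an unequal realised split. This objection stands, though the trial will be reported on one split that is known.
- **The word groups probably means the two methods.** A reader might infer that A is to be compared with B, which would say nothing about K-Lock. The Postoperatively paragraph uses the same word for the two securement methods when it describes time to drain removal, and Sample Size counts sites by method. The method reading is the natural one, although it still leaves pairing and side unspecified.
- **Side is not excluded.** The regression and the open clause could carry it. The accurate statement is that the plan does not specify side, not that it will never use it. Similarly, no balance rule is stated, which is not proof that none was used.
- **L may be small.** At 0.25 the loss is slight, and the documents offer no evidence on L. Sleeping side or a diseased breast mostly varies from patient to patient, and a side term removes only the consistent part.
- **It is second-order.** Pairing is the larger gap, and the primary outcome is feasibility with no powered hypothesis. Both are fair. They limit the weight of the point but do not justify leaving side out when pairing is written in.
- **Blocking may be too late.** The list was to be made before the study began, and the current text describes follow-up to previous study activities. Blocking is in any case the lesser part: a 20:20 list without a side term still loses power.

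**Conclusion.** The point holds as one about specification and precision. The plan randomises side, names tests that use neither pairing nor side, and states no balance rule. Under the assumptions above, the cost of omitting side from a paired analysis runs from slight (standard error 3% wider, power about 78%) to large (41% wider, power about 50%) as L goes from 0.25 to 1 SD. Given an unequal realised split, there is also a shift of 0.2 × L at 24:16 or 0.3 × L at 26:14.

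The power figures describe an assumed effect of 0.455 SD; they are not losses from a power that the protocol claims. Conservative error rates apply to a fixed 20:20 split, not to coin-toss allocation, so the two should not be combined. The change should be made because it is cheap and follows from the design, not because the documents show a left-right difference.

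**What to change.** Replace the between-groups sentence in the Analytical Plan with a statement that K-Lock and suture are compared within patient, with side (A/B) as a factor.

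- **Continuous outcomes:** take the equally weighted average of the A and B mean within-patient differences. If a patient has more than two drains, first form one K-Lock and one suture summary for that patient.
- **Binary outcomes:** use conditional logistic regression with method and side, or the Mainland-Gart test when events are sparse.
- **Reporting:** state how the list was generated, give the realised A/B split, and reconcile the bracketed 20 with the 40 pairs that the design yields.
- **Secondary:** block any part of the list that is still unused.

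The analysis change needs no new data, because A or B is already tied to each enrollment number, and it can be made before analysis even if enrolment is complete. It costs one degree of freedom (39 to 38), plus about 4% more variance at a 24:16 split if there is no left-right difference.

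### For low-rate drain events, a chi-square test without an interval cannot show how much worse K-Lock might be; report the within-patient risk difference with a paired 95% interval

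*Combined protocol and SAP*

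**What the plan says.** All of this is in the combined protocol and SAP.

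- **Objectives:** "To evaluate the feasibility, safety and efficacy of a novel suture-less drain securement device (K-Lock) via direct comparison to suture-based techniques". Comparative safety is therefore a stated aim. Under Outcome Measures, feasibility is primary and safety is secondary.
- **Interventions and Interactions:** "Patients will be randomized to either A) left side K-Lock with right side suture-based technique", or the reverse. Each patient carries both methods and is their own control.
- **Sample Size:** "We plan to enroll 40 patients allowing analysis of 80 (20 paired) drain sites". No power calculation, expected rate or margin goes with it.
- **Postoperative data:** "Safety of the novel drain device will be evaluated by inspecting device sites for instances of skin irritation at each office visit". Chart review adds "Accidental vs Planned drain removal", loosening, the need for re-securement and reinsertion.
- **Analytical Plan:** it opens with "Results will be analyzed initially using descriptive statistics", then says "Comparison between groups will be done using chi square tests for proportions". After t-tests, ANOVA and regression it ends with "Other inferential statistical analysis will be conducted as appropriate". It names no paired method for proportions, confidence interval, significance level or margin, and no rule for concluding on safety.

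**The concern.** The Background explains that early loss of a drain can lead to seroma or abscess. How much more often K-Lock might lose a drain than a suture is thus a question that the safety objective has to answer. A test of no difference returns only a p-value. When events are few it is often non-significant even if one method is clearly worse, and it does not say how large an excess remains possible. The ordinary chi-square test also treats the two sides of a patient as unrelated sites, which is not how they were randomised.

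At stake is what the trial can say at the end about accidental removal, reinsertion and similar items. If the reported comparison is a non-significant chi-square test, it cannot support a statement that the two methods are comparably safe.

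**Working it through.** **Inputs from the document.** 40 patients, one K-Lock side and one suture side each: 40 x 2 = 80 sites, which is 40 pairs. The printed figure of 20 pairs does not agree with this, so 40 is used and 20 is shown as a check. The plan gives no power figure to reproduce.

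**Assumptions.** Two-sided 5% level; suture rates of 5% to 20%; events on the two sides of a patient independent. None of these is in the document.

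**Power with 40 pairs.** Chi-square: sum the binomial probabilities of all outcomes (x of 40, y of 40) with uncorrected p < 0.05. Exact McNemar: sum over the number of discordant pairs, with discordance probability p_K(1 - p_S) + p_S(1 - p_K).

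| Suture v K-Lock | Chi-square | Exact McNemar |
|---|---|---|
| 5% v 10% | 15% | 4% |
| 5% v 15% | 35% | 18% |
| 10% v 20% | 25% | 15% |
| 10% v 30% | 63% | 51% |
| 20% v 60% | 97% | 94% |

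With 20 pairs, 5% v 15% falls to 15% and 3%.

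**Example: six K-Lock events, two suture events.** The observed rates are 6/40 = 15% and 2/40 = 5%.

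- Uncorrected chi-square = 80 x (6 x 38 - 34 x 2)² / (8 x 72 x 40 x 40) = 80 x 160² / 921,600 = 2.22, p = 0.14.
- Exact McNemar, all eight events in different patients: p = 2 x (1 + 8 + 28) / 2⁸ = 74/256 = 0.29.
- Risk ratio, treating sites as independent: 3.0, 95% interval 0.64 to 14.0.
- Within-patient difference: (6 - 2)/40 = +10 points. The 95% score interval for paired proportions is -4.6 to +25.3 points.

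Both tests report only that the difference is not significant. The interval adds that an excess of 25 points is not excluded.

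**Equal counts.** Two events on each side give a risk ratio interval of 0.15 to 6.8. The paired score interval is about ±12.5 points if all four events are discordant. Four on each side give a risk ratio interval of 0.27 to 3.7.

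**No K-Lock events.** For 0 of 40, the two-sided exact upper limit is 1 - 0.025^(1/40) = 8.8%.

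**The case against.** - **The plan does not rest on tests alone.** This is right. Descriptive statistics come first, photographs and patient surveys contribute to the safety assessment, and the closing clause leaves room for other methods. Raw counts would be visible whatever the p-value. None of this commits the study to an interval for the within-patient difference.
- **A reader might infer that a null result will be reported as equal safety.** The document does not say so. It speaks only of evaluating safety and makes no non-inferiority or equivalence claim. What stands is that a null test could not carry such a claim.
- **A reader might infer that every safety item is underpowered.** That rests on rarity, which is assumed. Skin irritation is the named safety measure, and the Background describes irritation as a known consequence of suture fixation. If it is common, a three-fold excess would probably be detected (20% v 60%: 94% to 97% power).
- **The verdict can depend on the test.** Five K-Lock losses against none give p = 0.0625 by exact McNemar but p = 0.021 by uncorrected chi-square. That pattern therefore does not show that the planned test would miss an excess. The 6 v 2 pattern is non-significant under both.
- **Feasibility is primary, and the rationale is improvement.** Modest precision on secondary items is acceptable in a study of this size, and a difference test suits a search for benefit. No larger sample is asked for. Low precision is itself a reason to show an interval.

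**Conclusion.** The point holds for low-rate items, chiefly accidental removal and reinsertion. At assumed suture rates of about 5% to 10%, a non-significant comparison on 40 pairs would leave a several-fold K-Lock excess open. A true tripling from 5% would be missed about 65% of the time by uncorrected chi-square and 82% by exact McNemar (100 - 35 and 100 - 18). From 10%, a tripling would be missed about 37% to 49% of the time.

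These sizes depend on assumed rates and on independence within the patient; the p-values and intervals for 6 v 2 depend only on the stated counts and, for the paired results, on all eight events being discordant. The point does not extend to skin irritation if that is common, and it does not show that the study team intends to read a null result as equal safety. It is a cheap improvement to the analysis, not an error that invalidates the trial.

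**What to change.** In the Analytical Plan, for accidental removal, loosening or re-securement, reinsertion and skin irritation:

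- Replace the chi-square comparison as the main reported result with the within-patient risk difference (K-Lock minus suture) and its 95% score interval for paired proportions.
- Give the event rate for each method with an exact 95% interval.
- Base the safety conclusion on the upper limit of the difference, that is, the largest K-Lock excess not excluded, and not on non-significance.
- Correct the count of pairs in Sample Size so that the denominator is clear.

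No enrolment, procedure or data collection changes, because side and patient are already recorded. The cost is a few lines of plan wording and a more limited safety statement than a bare non-significant test might suggest.
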